### **6.3.3 Criteria for First Administration of 5-FC (and leucovorin)**

For Cycle 1 Day 4 5-FC (and leucovorin) administration to proceed, the participant must have recovered well from any immediate post-operative effects **and** requires no more than 16 mg/day of dexamethasone. Otherwise the participant will be removed from treatment. Criteria found in Section 6.3 (Dose modifications) also apply.

### **6.3.4 Dose Modifications**

Table 6.3.4 details the criteria for disrupting treatment, dose modification and treatment discontinuation following an adverse event. See section 6.3.1 for general guidelines. The agent listed in Table 6.3.4 indicates the drug to which the toxicity is likely attributed based on previous trials of 5-FC (with leucovorin) and possible anticipated toxicities to the CD-NSCs.

**Table 6.3.4 Criteria for Disrupting Treatment, Dose Modification or Discontinuation**

Adverse Event	Agent most likely attributed to toxicity	Treatment modification
Immune Response to NSCs (i.e. development of a new neurologic deficit not attributed to the location of brain tumor, fever without localizing source of infection, new or progressive rash, cough etc.)		
Grade 2 allergic reaction to the NSCs.  NOTE: a decision to stop study treatment will be based on development of clinical signs/symptoms of an immune response rather than a particular level of anti-NSC T cells or antibodies.	NSCs	
Hold study treatment.
 
Initiate immunological testing: Take 3-5 ml of blood in red top tube, kept upright at room temperature until delivery to CICSL. Store at 4 C after sample clots if unable to deliver sample the same day. Take additional samples (at least one additional sample) every two days.
 
Initiate pharmacologic management for an allergic reaction: Restart dexamethasone to a dose of 4 mg twice daily; if patient is already taking dexamethasone, then increase dexamethasone to at least 4 mg twice daily.
 
Hold study treatment until sign/symptoms <math>\leq</math> grade 1, and resume treatment at the same dose, while continuing dexamethasone at a dose determined by the discretion of the treating investigator in consultation with the PI.

Grade 3 or 4 allergic reaction to NSCs  NOTE: a decision to stop study treatment will be based on development of clinical signs/symptoms of an immune response rather than a particular level of anti-NSC T cells or antibodies.	NSCs	
Hold study treatment.
 
Initiate immunological testing: Take 3-5 ml of blood in red top tube, kept upright at room temperature until delivery to CICSL. Store at 4 C after sample clots if unable to deliver sample the same day. Take additional samples (at least one additional sample) every two days.
 
Initiate pharmacologic management for an allergic reaction: Restart dexamethasone to a dose of 4 mg twice daily; if patient is already taking dexamethasone, then increase dexamethasone to at least 4 mg twice daily. Continue dexamethasone until event resolves to <math>\leq</math> Grade 1, and thereafter at a dose determined by treating investigator as clinically indicated.
 
If an immune response to the NSCs is considered at least possible, discontinue study treatment.

Hematological Toxicities		
Thrombocytopenia Grade 1 ( $75 \times 10^9/L < LLN$ )	5-FC (with leucovorin)	Hold treatment until recovery to $\geq 100 \times 10^9/L$ . Resume at pre-hold dose.
Thrombocytopenia Grade 2 ( $50 - < 75 \times 10^9/L$ )	5-FC (with leucovorin)	Hold treatment until recovery to $\geq 100 \times 10^9/L$ . Resume at pre-hold dose.
Thrombocytopenia Grade 3 ( $25 - < 50 \times 10^9/L$ )	5-FC (with leucovorin)	Hold treatment until recovery to $\geq 100 \times 10^9/L$ .
	5-FC (with leucovorin)	
For patients not taking leucovorin: Resume treatment with a 25% dose reduction of 5-FC of the pre-hold dose.
 
For patients taking leucovorin: First event: resume treatment at the same dose of NSCs and 5-FC, and permanently discontinue leucovorin. Second event: resume treatment with a 25% dose reduction of 5-FC of the pre-hold dose.

Thrombocytopenia Grade 4 ( $<25 \times 10^9/L$ )		
Hold treatment until recovery to <math>\geq 100 \times 10^9/L</math>.
 
For patients not taking leucovorin: Resume treatment with a 25% dose reduction of 5-FC of the pre-hold dose.
 
For patients taking leucovorin: First event: resume treatment at the same dose of NSCs and 5-FC, and permanently discontinue leucovorin. Second event: resume treatment with a 25% dose reduction of 5-FC of the pre-hold dose.

Neutropenia (ANC) Grade 1 ( $1.5 \times 10^9/L < LLN$ )	5-FC (with leucovorin)	Maintain treatment.
Neutropenia (ANC) Grade 2 ( $1.0 - < 1.5 \times 10^9/L$ )		Maintain treatment.
Neutropenia (ANC) Grade 3 ( $0.5 - < 1.0 \times 10^9/L$ )		
Hold treatment until recovery to <math>\leq</math> grade 2 (<math>ANC \geq 1.0 \times 10^9/L</math>). Resume treatment with no dose modifications. Consider administration of GCSF.

Neutropenia (ANC) Grade 4 ( $< 0.5 \times 10^9/L$ )		
Administer GCSF. Hold treatment until recovery to <math>\leq</math> grade 2 (<math>ANC \geq 1.0 \times 10^9/L</math>). Resume treatment with no dose modifications. Continue administration of GCSF.

Lymphocytopenia Grade 1-3	5-FC (with leucovorin)	Maintain treatment
Lymphocytopenia Grade 4 ( $< 0.800 \times 10^9/L$ )		
Check CD4 lymphocyte level. If <math>< 0.200 \times 10^9/L</math> initiate PCP prophylaxis. Maintain treatment.

Serum Electrolytes		
Serum Electrolytes $\geq$ Grade 3 Calcium, Potassium, Magnesium, Phosphorous	5-FC (with leucovorin)	Correct electrolyte deficits. Maintain treatment per investigator discretion.
Renal Toxicity Use Cockcroft & Gault formula and actual body weight to determine calculated creatinine clearance		
Calculated creatinine clearance 21.0 ml/min – $< 51.0$ ml/min	5-FC	Increase 5-FC interval to Q12 hours; if leucovorin is being administered, increase leucovorin interval to Q12 hours.
Calculated creatinine clearance 10.0 ml/min – $< 21.0$ ml/min		Increase 5-FC interval to Q24 hours; if leucovorin is being administered, increase leucovorin interval to Q24 hours.
Calculated creatinine clearance $< 10.0$ ml/min		Increase 5-FC interval to Q48 hours; if leucovorin is being administered, increase leucovorin interval to Q48 hours.
Gastrointestinal		
Diarrhea Grade 1 (2-3 stools/day $>$ pretreatment)	5-FC (with leucovorin)	Maintain treatment
Diarrhea Grade 2 (4-6 stools/day $>$ pretreatment)		Hold both study drugs until resolved to $\leq$ grade 1, then resume treatment at pre-hold dose
Diarrhea Grade 3 (7-9 stools/day $>$ pretreatment) while on optimal anti-diarrhea therapy		Hold study treatment until the diarrhea decreases to $\leq$ grade 1
		
For patients not taking leucovorin Restart treatment with a 25% decrease in 5-FC from the pre-hold dose.
 
For patients taking leucovorin First event: resume treatment at the same dose of NSCs and 5-FC, but permanently discontinue leucovorin. Additional events: resume treatment with a 25% dose reduction of 5-FC from the pre-hold dose.

Diarrhea Grade 4 (≥10 stools/day > pretreatment) while on optimal anti-diarrhea therapy	5-FC (with leucovorin)	Hold study treatment until the diarrhea decreases to ≤ grade 1  For patients not taking leucovorin Restart treatment with a 25% decrease in 5-FC from the pre-hold dose.  For patients taking leucovorin First event: resume treatment at the same dose of NSCs and 5-FC, but permanently discontinue leucovorin. Additional events: resume treatment with a 25% dose reduction of 5-FC of the pre-hold dose.
Vomiting or Nausea Grade 1		Maintain treatment
Vomiting or Nausea Grade 2		Maintain treatment
Vomiting or Nausea Grade 3, despite maximal medical management		Hold study treatment until resolution to ≤ grade 1  For patients not taking leucovorin First event: resume treatment at pre-hold dose. Additional events: restart treatment with a 25% decrease in 5-FC from the pre-hold dose.  For patients taking leucovorin First event: resume treatment at pre-hold dose. Second event: resume treatment at the same dose of NSCs and 5-FC, but permanently discontinue leucovorin. Additional events: resume treatment with a 25% dose reduction of 5-FC of the pre-hold dose.
Vomiting Grade 4, despite maximal medical management		Hold study treatment until resolution to ≤ grade 1  For patients not taking leucovorin Restart treatment with a 25% decrease in 5-FC from the pre-hold dose.  For patients taking leucovorin First event: resume treatment at the same dose of NSCs and 5-FC, but permanently discontinue leucovorin. Additional events: resume treatment with a 25% dose reduction of 5-FC of the pre-hold dose.
Nervous System Disorders		
Grade 3 Nervous System Disorder that is not attributable to tumor location or neurosurgery and is considered a least possibly attributable to NSCs, 5-FC, or leucovorin, or any combination and is not an immune response to study agents.	NSCs, 5-FC, leucovorin	Hold treatment until resolution to ≤ grade 1.  First event: If resolves within 7 days, resume treatment at pre-hold dose.  If does not resolve within 7 days, resume treatment with a dose reduction of NSCs and 5-FC by 25% of the pre-hold dose. If the patient is taking leucovorin, discontinue leucovorin.*  Second event: Resume treatment with dose reduction of NSCs and 5-FC by 25% of the pre-hold dose. If the patient is still taking leucovorin, discontinue leucovorin.*  *If the temporal association implicates NSCs or 5-FC (and leucovorin) rather than both/all agents, dose reductions may apply only to the implicated agent.

Grade 4 Nervous System Disorder that is not attributable to tumor location or neurosurgery and is considered a least possibly attributable to NSCs, 5-FC, or leucovorin, or any combination and is not an immune response to study agents.		Hold until $\leq$ grade 1, then perform brain MRI. If objective evidence of clinical benefit, restart treatment with a dose reduction of NSCs and 5-FC by 25% of pre-hold dose, and, if patient is taking leucovorin, discontinue leucovorin.* If no objective evidence of clinical benefit is seen on MRI then, discontinue treatment.  *If the temporal association implicates NSCs or 5-FC (and leucovorin) rather than both/all agents, dose reductions may apply only to the implicated agent.
Other Unspecified Non-Hematologic Toxicities Considered Related Only to 5-FC (with Leucovorin)		
Grade 1		Maintain treatment
Grade 2		Maintain treatment
Grade 3		Hold study treatment until resolution to $\leq$ grade 1  For patients not taking leucovorin Restart treatment with a 25% decrease in 5-FC from the pre-hold dose.  For patients taking leucovorin First event: resume treatment at the same dose of NSCs and 5-FC, but permanently discontinue leucovorin. Additional events: resume treatment with a 25% dose reduction of 5-FC of the pre-hold dose.
Grade 4		Hold study treatment until resolution to $\leq$ grade 1  For patients not taking leucovorin Restart treatment with a 25% decrease in 5-FC from the pre-hold dose.  For patients taking leucovorin First event: resume treatment at the same dose of NSCs and 5-FC, but permanently discontinue leucovorin. Additional events: resume treatment with a 25% dose reduction of 5-FC of the pre-hold dose.
Other Unspecified Non-Hem Toxicities Considered Related Only to NSCs		
Grade 1		Maintain treatment
Grade 2		Maintain treatment
Grade 3		Hold until $\leq$ grade 1, then dose reduce NSCs by 25%; resume treatment with same dose of 5-FC and leucovorin.
Grade 4		Hold until $\leq$ grade 1, then perform brain MRI. If objective evidence of clinical benefit, restart treatment at pre-hold doses of 5-FC and leucovorin and a dose reduction of NSCs by 25% of the pre-hold dose of NSCs. If no objective evidence of clinical benefit is seen on MRI then discontinue treatment.
Other Unspecified Non-Hem Toxicities Considered Related to a Combination of NSCs and 5-FC (with Leucovorin)		
Grade 1	NSCs with	Maintain treatment
Grade 2	5-FC (and	Maintain treatment

Grade 3	leucovorin)	
Hold treatment until resolution to <math>\leq</math> grade 1.
 
First event: If resolves within 7 days, resume treatment at pre-hold dose.
 
If does not resolve within 7 days, resume treatment with then dose reduce NSCs and 5-FC by 25% from the pre-hold dose. If the patient is taking leucovorin, discontinue leucovorin.
 
Second event: Resume treatment with dose reduction of NSCs and 5-FC by 25% of pre-hold dose. If the patient is taking leucovorin, discontinue leucovorin.

Grade 4		
Hold until <math>\leq</math> grade 1, then perform brain MRI. If objective evidence of clinical benefit, restart treatment with a dose reduction of NSCs and 5-FC by 25% of pre-hold dose, and, if patient is taking leucovorin, discontinue leucovorin. If no objective evidence of clinical benefit is seen on MRI then, discontinue treatment.

Other Unspecified Non-Hem Toxicities Considered UNRELATED to Study Agents		
Other unspecified events of any grade considered unlikely to be related or not related to study agents.	UNRELATED	Maintain treatment with study agents. Interruption of study treatment is permitted if the investigator consults with the Principal Investigator to determine that this is in the best interest of the participant.

## 6.4 Adjustments to the Treatment Cycle Following an Interruption in Agent Administration

The day count continues despite a hold in agent administration.

Should a hold or delay in treatment occur, evaluations required by the protocol (see Section 5 and 10) will be conducted at the original times during the cycle and safety assessments relevant to the toxicity will be repeated prior to resuming agent administration.

The timing of resumption (whether in the same cycle or as part of the subsequent cycle) depends on where in the cycle agent was held, and when criteria to resume are met. Details are described in the sections that follow.

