#### **5.2.7 Cycle 1 Days 18-24: Administration of 5-FC (and leucovorin for dose level 4 patients)**

Dosing of 5-FC (and possibly leucovorin) as per the dose level the patient is on (see the dose escalation schema table in section 5.1)

Prochlorperazine 10 mg p.o. every 6 hours (or a similar strength anti-emetic) will be used as needed.

Study patients will be evaluated by their treating physicians in clinic on day 22 (as per section 10.0 Study Calendar).

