#### 6.2.3.2 5-FU

**Per the package insert for systemic 5-FU, the expected toxicities for 5-FU are as follows, where the asterisk (\*) signifies a common event:**

*Cardiovascular:* myocardial ischemia, angina,

*Eye disorders:* photophobia, visual changes, lacrimation, lacrimal duct stenosis.

*Gastrointestinal:* stomatitis\*, esophagopharyngitis\*, diarrhea\*, anorexia\*, nausea\*, vomiting\*, gastrointestinal ulceration and bleeding.

*Hematologic:* leucopenia\* (nadir: days 9-14; recovery by day 30),, pancytopenia, thrombocytopenia, agranulocytosis, anemia.

*Immune system disorders:* anaphylaxis and generalized allergic reactions.

*Nervous system disorders:* acute cerebellar syndrome (which may persist following discontinuance of treatment), nystagmus, headache.

*Skin and subcutaneous tissue disorders:* alopecia\*, dermatitis (most commonly pruritic maculopapular rash)\*, dry skin; fissuring; photosensitivity, as manifested by erythema or increased pigmentation of the skin; vein pigmentation; palmar-plantar erythrodysesthesia syndrome, as manifested by tingling of the hands and feet followed by pain, erythema and swelling (hand-foot syndrome); nail changes (nail loss)

*Psychiatric:* disorientation, confusion, euphoria.

*Respiratory:* epistaxis.

*Miscellaneous:* thrombophlebitis.

Severe toxicity (such as stomatitis, diarrhea, neutropenia, and possibly neurotoxicity) associated with 5-FU has been attributed to deficiency of dipyrimidine dehydrogenase activity.

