### 6.4.1 Holding Day 15 NSCs

If Day 15 NSCs and subsequent 5-FC (with leucovorin) are held, resultant start dates are as follows:

- If participant is able to resume treatment by or on Day 22, he/she will resume study agents as soon as logistically feasible during the same treatment cycle. The cycle length would be extended accordingly, so that 14 days between NSC administrations would be maintained.
- If participant is not able to resume treatment by or on Day 22, he/she will continue the current cycle without a second NSC administration and resume study agents at the start of the next treatment cycle. The current cycle would be 28 days in length and the participant will forgo the Day 15 NSCs/ Day 18-24 5-FC (w/ w/o leucovorin).

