### 7.2 Monitoring and Personnel Responsible for Monitoring

The City of Hope Protocol Management Team (PMT) consisting of the PI, collaborating investigators, CRA, protocol nurse, and statistician is responsible for monitoring the data and safety of this study, including implementation of the stopping rules for safety.

This study will utilize the Phase I tracking log to monitor data and safety for dose escalation, recording doses administered and resultant adverse events. The tracking log will contain dose levels administered, DLT-defining adverse events, and documentation that the data from a dose level is complete before dose escalation. Those data and safety elements will be reported to the COH DSMC as applicable with the PMT report, which will be submitted quarterly from the anniversary date of activation, as noted in Table 1 below. Protocol specific data collection will include the following items: adverse events per dose level, patient outcomes, and protocol deviations.

A decision to escalate to the next dose level will be made by the PMT only after all patients on the current dose level have been observed through day 28. Enrollment of the first 3 patients to dose levels 1-3 will be staggered by requiring that each of these patients be observed for 28 days before the next patient can begin treatment on a particular dose level.

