### 8.2.4 Pharmacokinetic Data

5-FC is rapidly and well absorbed. Its oral bioavailability is 78-90%. There is no significant systemic metabolism of 5-FC. More than 90% is excreted by glomerular filtration as unchanged drug. The systemic half-life is 2.5 to 6 hours. The time to peak concentration is 1-2 hours. Distribution: 5-FC distributes widely in body water. Less than 4% is protein-bound. Levels in the cerebrospinal fluid are approximately 80% of serum levels.

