## 10.0 Study Calendar

	Screening 	Cycle 1						Cycle 2 			Off Tx Visit 	30-Day Post Tx Visit 
		Day 1	Day 2	Days 4-10	Day 15	Days 18-24		Day 1 and Day 15	Days 4-10 and 18-24	Day 28 		
H&P, Neuro Exam, KPS	X				X	X 		X			X	X 
Informed consent	X 											
HLA antibody screening	X 											
Brain MRI	X 	X 	X 	X						X 	X 	
Non-contrast brain CT		X 										
Toxicity assessment			X		X	X 		X			X	X
Collection of blood samples for immunologic correlative studies	X 				X 			X 			X	
WBC with ANC, hgb, plts	X			X 	X	X 		X			X	
Serum chemistries and LFTs	X			X 	X	X 		X			X	
PT/PTT	X											
EKG	X											
CXR	X											
Urine or serum pregnancy test	X											
Tumor resection or biopsy		X										
Placement of a Rickham catheter		X										
Intracerebral administration of CD-expressing NSCs		X 			X 			X 				
Placement of a microdialysis catheter 		X										
Administration of 5-FC (and leucovorin, as indicated)				X		X			X			
Collection of Dialysate Samples for Measuring Intracerebral Levels of 5-FC, LV, and 5-FU 				X 								
Collection of Blood Samples for 5-FC, LV, and 5-FU Levels 				X 								
RCR testing	X 											

Study tests and procedures may be done +/- 3 days for patient convenience and scheduling. A window period of +/- 1 day is allowed for intracranial administration of NSCs, but there must still be at least an interval of at least

3 days between administration of the NSCs and start of the 7-day course of 5-FC (if a patient receives NSCs 1 day earlier, then it is acceptable to wait 4 days before the patient starts taking the 5-FC).

- 1 Only dose level 4 patients will undergo intracerebral microdialysis.
- 2 All screening assessments to be performed within 14 days prior to start of treatment (day of surgery), except for the brain MRI which can be performed within 28 days of registration, and except for signing of the informed consent document and HLA antibody screening, which can be done outside the 14 day window prior to start of study treatment.

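### If the cycle 1 day 15 NSC dose is given 4 to 7 days late in the same cycle, the day 22 visit stays put while the 5-FC course moves, so the one planned on-course check comes before the course or early in it (minor)

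*Combined protocol and SAP*

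**What the plan says.** Section 6.4 keeps the day count running through a hold and states that "evaluations required by the protocol (see Section 5 and 10) will be conducted at the original times during the cycle". The one check it adds is a repeat, before resumption, of the safety assessments that bear on the toxicity in question.

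Section 6.4.1 covers a held day 15 NSC dose. A patient who can resume by day 22 receives the NSCs and the 5-FC in the same cycle: "The cycle length would be extended accordingly, so that 14 days between NSC administrations would be maintained". The Study Calendar (section 10.0) requires at least 3 days between NSCs and the start of 5-FC, so the course moves with the dose.

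In cycle 1 the calendar marks toxicity assessments on days 2, 15 and 22. Blood counts and chemistries after screening are on day 3 (footnote 12), day 15 and day 22 (footnote 17). Section 5.2.7 also places a clinic evaluation on day 22. The 5-FC courses are on days 4-10 and 18-24. The calendar adds a general window: "Study tests and procedures may be done +/- 3 days for patient convenience and scheduling".

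Under section 5.5 the DLT period runs through the cycle 2 day 1 safety assessments.

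**The concern.** By planned day, day 22 is the only toxicity and laboratory check that falls inside a 5-FC course during the DLT period. Section 6.4 fixes it to the calendar, while section 6.4.1 moves the course it was meant to observe. After a long enough delay it becomes a pre-course check, and nothing replaces it during the course.

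The rules in Table 6.3.4 can change a course only while doses remain. For example, a calculated creatinine clearance below 51 ml/min but at least 21 ml/min leads to "Increase 5-FC interval to Q12 hours", and lower values to Q24 or Q48 hours. Section 8.2.4 says of 5-FC: "More than 90% is excreted by glomerular filtration as unchanged drug". Platelet falls and grade 2 or worse diarrhea call for a hold. If such a change starts during the resumed course, the next planned check is cycle 2 day 1, after the last dose. Some of these patients will have been delayed because of toxicity, and for them an on-course check is most useful.

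**Working it through.** **Inputs.** NSC dose 2 on day 15 and 5-FC on days 18-24, every 6 hours (sections 5.1 and 5.7). NSC-to-5-FC interval of 3 days (section 10.0 gives this as a minimum). Visit on day 22, window ±3 days (section 10.0). 14 days between NSC doses kept, and resumption possible by day 22, so d is taken as 0 to 7 (section 6.4.1).

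**Formulas.** NSC day = 15+d. Course = days 18+d to 24+d. Cycle 2 day 1 = 29+d. Day x is course day x − (18+d) + 1. Doses per course = 4 × 7 = 28.

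**The plan's own schedule (d = 0).** Course days 18-24; day 22 is course day 22 − 18 + 1 = 5; cycle 2 day 1 is day 29. This agrees with the protocol. On earlier course days 4 × 4 = 16 doses have been scheduled, leaving 28 − 16 = 12 (43%) that the visit can still change.

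**With a delay.**

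| d | NSC day | 5-FC days | Day 22 falls on | Day 25 (full +3) falls on | Cycle 2 day 1 | Days from day 22 to cycle 2 day 1 |
|---|---|---|---|---|---|---|
| 0 | 15 | 18-24 | course day 5 | 1 day after | 29 | 7 |
| 3 | 18 | 21-27 | course day 2 | course day 5 | 32 | 10 |
| 4 | 19 | 22-28 | course day 1 | course day 4 | 33 | 11 |
| 5 | 20 | 23-29 | 1 day before | course day 3 | 34 | 12 |
| 6 | 21 | 24-30 | 2 days before | course day 2 | 35 | 13 |
| 7 | 22 | 25-31 | 3 days before | course day 1 | 36 | 14 |

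- Course day 5 is calendar day 22+d. The +3 window reaches it for d ≤ 3, so those delays need no rule. At d = 4 it is day 26, one day outside the window.
- For d = 5, 6, 7, day 22 is also 2, 1, 0 days after the NSC dose. No 5-FC dose of that course has been taken, so all 28 can still be changed on the result.
- On day 25, the doses scheduled on earlier course days number 4 × (7 − d) = 8, 4, 0.
- Cycle 2 day 1 is (29+d) − (24+d) = 5 days after the last 5-FC day, for every d. It is course day 12, inside the leucopenia timing that section 6.2.3.2 gives for systemic 5-FU ("nadir: days 9-14; recovery by day 30"), if that is counted from the start of the course.
- A visit moved to day 22+d falls on course day 5 for every d, with 12 of 28 doses left, as in the undelayed plan.

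**The case against.** The strongest reply is that the protocol does not treat an on-course check as standard. The cycle 1 day 4-10 course has laboratory tests on day 3 only, and from cycle 2 on the assessments are on days 1 and 15. A patient delayed 5 to 7 days therefore gets the pattern that every other course has. This stands, and it is a main reason the point is minor. It remains true that the plan puts one check inside a course in the DLT period and that section 6.4 displaces it.

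A second reply is that a day 22 check before the course has value of its own. Fresh counts and creatinine can set the whole course, whereas in the undelayed plan the last pre-course tests are on day 15 and 16 doses precede day 22. Recovery criteria must also be met before resumption. This stands too: the loss is confined to changes that begin after the course has started.

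Three stronger readings are tempting, and the documents support none of them.

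- A reader might infer that DLTs go uncounted or that escalation proceeds on incomplete data. Cycle 2 day 1 moves with the extended cycle, section 5.5 includes its assessments in the DLT period, and section 5.6 requires follow-up through them (or a DLT) before a patient counts for escalation.
- A reader might infer that the next staggered patient may start while the delayed patient is still on 5-FC, because section 7.2 asks that "each of these patients be observed for 28 days before the next patient can begin treatment on a particular dose level" and day 29 is course day 12 − d = 7, 6, 5 for d = 5, 6, 7. But section 5.6.4 also names the end of the DLT assessment period, and section 13.2 has patients at dose levels 1-3 enter after the previous one completes cycle 1, which section 6.4.1 lengthens. What is left is a wording mismatch in section 7.2.
- A reader might infer that delayed patients go unmonitored. They have the pre-resumption check, the day 22 visit and cycle 2 day 1, and nothing bars an unscheduled check.

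**Conclusion.** The point holds as a minor safety-monitoring gap in one contingency. For d = 5 to 7 the planned on-course check falls 1 to 3 days before the course, or on course day 3, 2 or 1 at best. For d = 4 it falls on course day 1, or day 4 at best. The cost is later detection of changes that start during the resumed course, such as falling creatinine clearance, falling counts or diarrhea. From a day 22 visit the wait to cycle 2 day 1 is 11 to 14 days instead of 7, and by then that course can no longer be changed. The DLT count and the escalation decision are unaffected.

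This rests on three assumptions: original times means calendar cycle days, as the running day count implies; 5-FC starts exactly 3 days after the late NSC dose, since section 6.4.1 does not give the new 5-FC dates; and d does not exceed 7. The documents do not say how often delays of 4 to 7 days occur, and no frequency is assumed.

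**What to change.** In sections 6.4 and 6.4.1 and calendar footnote 17, state that when the day 15 NSCs are given late in the same cycle, the day 22 visit and laboratory tests are done 7 days after the actual NSC dose (day 22+d, course day 5).

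State also that the check before resumption includes toxicity assessment, counts and chemistries, whatever caused the hold. Without this, moving the visit would give up the pre-course check: at d = 7 the last planned full laboratory tests would be on day 15, which is 25 − 15 = 10 days before the course. With it, the full checks at d = 7 are on days 15, about 22, 29 and 36, and none is lost.

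As a wording alignment only, replace the fixed 28 days and day 28 in section 7.2 with the end of the DLT assessment period (the cycle 2 day 1 safety assessments), to agree with sections 5.6, 5.6.4 and 13.2.

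The cost is a few sentences, minor rescheduling and slightly fuller checks before resumption.
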